7.6.3 Primary Efficacy Analysis

The primary efficacy endpoint is mean change in the weekly number of UI episodes from study baseline to Week 6 after the first treatment. Seven-day bladder diaries that contain data recorded on at least 5 days will be included in the analysis.

As all subjects should have visits up to and including week 12, but thereafter visits are dependent on whether the subject receives retreatment, statistical testing between treatment

Statistical Analysis Plan

Version: Final v1.0

September-2018

Ipsen Protocol No. D-FR-52120-223

000000146513

Date of Issue: 21-

Covance Study ID:

groups will be performed only up to Week 12, inclusive. Descriptive statistics table will present any timepoint.

Weekly number of UI episodes and the mean change from study baseline will be presented for the DBPC Cycle. The mixed model repeated measures (MMRM) analysis will be conducted with the change of the weekly number of UI episodes from study baseline as response variable. Fixed effect variables include treatment group, visit (Week 2, Week 6 and Week 12), treatment-by-visit interaction, stratification variables [the aetiology of NDO and prior intradetrusor BTX-A usage for UI] and study baseline value of weekly number of UI episodes. Random effect will include the subject effect. An unstructured covariance matrix will be specified in the mixed model to account for within subject correlation. If model fails to converge, the structure of first order autoregressive AR (1), compound symmetry (CS) or variance components (VC) will be used.

The least square means (LSMEANS) of the change of weekly number of UI at each visit in each group with standard error, the difference of mean between the two treatment groups at each visit, the 95% CI of the difference and the p-value for treatment group will be presented. The comparison of main interest will be treatment difference at Week 6.

The SAS codes of MMRM for reference are below.

CCI
[Redacted SAS code]

The validity of the model assumptions of normality will be investigated using residual plots. The LS means of change from study baseline for weekly UI in the DBPC and Dysport Cycles will be presented in line plots by treatment groups.

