2.3 Sample Size and Power

The sample size is based on the ability to detect a statistically significant treatment difference in the weekly number of UI episodes at Week 6 following the first IMP administration in the two Dysport arms (600 U and 800 U) compared to the placebo arm.

Assuming a weekly decrease of 21 UI episodes in each Dysport arm and a weekly decrease of 12 UI episodes in the placebo arm, with a common standard deviation of 20 UI episodes, 80% power, and an alpha of 0.025 (as testing of both the 600 U and 800 U doses vs. the placebo dose will be performed simultaneously), a sample size of 96 subjects per dose group (a total of 288 subjects) is needed. Dropout between randomisation and Week 6 (primary efficacy timepoint) is expected to be 10%, and thus a total of 318 subjects would be needed to be enrolled. However, in order to ensure that the development program will deliver adequate Dysport exposure data to meet ICH E1 guideline recommendations, a total of 330 subjects are planned to be randomised. Subjects who leave the study early will not be replaced.

Sample size calculations were performed in SAS Studio 3.6.

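### The primary MMRM's fallback covariance list is unordered and every entry assumes equal variance at all visits; the random subject effect alongside an unstructured matrix is redundant and could trigger the fallback needlessly

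*SAP*

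**What the plan says.** SAP 7.6.3 defines the confirmatory model as an MMRM for change from baseline in weekly UI episodes. On its terms it says: "Fixed effect variables include treatment group, visit (Week 2, Week 6 and Week 12), treatment-by-visit interaction", together with the two stratification factors and the baseline count. Two consecutive sentences then set the covariance: "Random effect will include the subject effect. An unstructured covariance matrix will be specified in the mixed model to account for within subject correlation". The contingency follows: "If model fails to converge, the structure of first order autoregressive AR (1), compound symmetry (CS) or variance components (VC) will be used". On the estimand of interest the section says: "The comparison of main interest will be treatment difference at Week 6".

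The reference SAS code under this text is redacted, which is not a fault of the plan. The readable text gives no order among the three fallbacks, no version with unequal variances, and no robust standard error. SAP 7.6.4.2 plans a Week 6-only ANCOVA as a sensitivity analysis.

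**The concern.** Two things look wrong, and they differ in weight.

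The lesser one is the over-parameterised model. An unstructured 3×3 matrix leaves nothing for a subject variance to explain. Fitted literally, the software may report a singular Hessian or a zero subject variance, and an analyst might treat that as the failure to converge that the next sentence provides for.

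The greater one is what happens then. The target is a single-visit contrast, but each listed structure estimates one variance across all three visits and applies it to Week 6. Also, a model with treatment terms can fail to converge only when it is fitted to treatment-coded data, so an unordered list leaves a choice among structures that could be made with results in view.

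At stake are the two primary p-values. They enter the Hochberg step and decide whether, and at what level, the ordered secondary endpoints are tested (SAP 7.6.2). The same model serves the I-QoL endpoint (7.6.5), the per-protocol and mis-stratification analyses (7.6.4.1, 7.6.4.4) and the primary-endpoint subgroups (7.6.7).

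**Working it through.** **Inputs from the documents.** SAP 2.3 takes mean reductions of 21 episodes a week on either dose and 12 on placebo, and arrives at 96 per group. Its spread and error rates read: "with a common standard deviation of 20 UI episodes, 80% power, and an alpha of 0.025". The difference is 21 − 12 = 9. Protocol 9.2 makes the 0.025 two-sided.

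**Inputs that are assumptions.** The documents give one SD, 20, taken here as the SD of change at Week 6. They give no SD for Week 2 or Week 12 and no within-subject correlation. Those are varied below.

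**1. The plan's own figure.** Normal approximation: n = 2 × (20/9)² × (2.241 + 0.842)² ≈ 94 per group. The t-based calculation gives power 0.799 at 95 and 0.804 at 96, so 96 reproduces. The sample size is not in question. When the Week 6 variance is estimated on its own, the standard error is 20 × √(2/96) = 2.89.

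**2. Identifiability.** Write the marginal covariance as V = R + σ²J, where R is unstructured and J is a matrix of ones.
- Unstructured plus subject effect: 7 parameters, 6 distinct elements of V, rank 6. Only the split between R and σ² is lost.
- CS plus subject effect: 3 parameters, rank 2, so again redundant.
- VC plus subject effect: this is CS.
- VC without the subject effect: within-subject correlation is set to zero. Weeks 2 and 12 then say nothing about a missing Week 6 value, which weakens the missing-at-random argument of SAP 6.2.1.1.

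The treatment contrast and its standard error depend on V alone, so the redundancy does not move them. As a check, 60 trials were simulated (96 per arm in two arms, SDs 14/20/18, correlation 0.6, 10% of visits missing at random) and fitted by REML with and without the subject effect. Both fits converged in all 60, and the Week 6 estimates and standard errors agreed to within 0.001. The optimiser was not SAS, which may behave differently on a singular Hessian.

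**3. Effect of an equal-variance fallback.** For CS and VC with complete data:

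SE ratio = √(mean of the three visit variances) / Week 6 SD

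true level of a nominal 0.05 test = 2 × [1 − Φ(1.96 × ratio)]

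Worked case (14, 20, 18): mean variance = (196 + 400 + 324)/3 = 306.7; square root 17.51; ratio 17.51/20 = 0.876; 1.96 × 0.876 = 1.716; level 0.086.

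| Assumed SDs, Weeks 2, 6, 12 | Mean variance | SE ratio | True level of a 0.05 test |
|---|---|---|---|
| 14, 20, 18 | 306.7 | 0.876 | 0.086 |
| 15, 20, 20 | 341.7 | 0.924 | 0.070 |
| 18, 20, 19 | 361.7 | 0.951 | 0.062 |
| 20, 20, 20 | 400.0 | 1.000 | 0.050 |
| 16, 20, 24 | 410.7 | 1.013 | 0.047 |
| 22, 20, 24 | 486.7 | 1.103 | 0.031 |

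**4. AR(1).** The formula is only approximate here, so the best-fitting AR(1) matrix was found numerically for true correlations of 0.5 and 0.7. For (16, 20, 16), CS and VC give ratio 0.872 and level 0.088; AR(1) gives 0.849 to 0.861 and 0.091 to 0.096. For (24, 20, 24), CS and VC give ratio 1.137, level 0.026 and power 0.715 at alpha 0.025; AR(1) gives 1.150 to 1.163, 0.023 to 0.024, and power about 0.70 to 0.71. Power with the correct standard error, by the same normal approximation, is 0.81. AR(1) therefore departs a little further than CS or VC, in the same direction.

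**The case against.** The strongest reply is that none of this may ever matter. A plain unstructured matrix has six parameters for roughly 290 to 330 subjects, and non-convergence would be unusual. The random-effect sentence may be loose wording for the subject grouping in the repeated-measures statement, and the redacted code could show that. Even fitted literally, the redundant term leaves the Week 6 result unchanged, and a singular-Hessian note is not necessarily a failure to converge. The level figures rest on SDs that the documents do not give, and the Week 6 ANCOVA would expose a distorted standard error.

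Most of this stands, and it rules out three stronger readings that a reader might infer. The first is that the primary model cannot be estimated or that its Week 6 test is invalid: only the split of the covariance is unidentified. The second is that the fallback is likely: nothing in the documents gives its probability. The third is that the type I error is inflated: the error can go either way, and it vanishes when the Week 6 variance equals the visit average.

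Two things remain. The fallback list is defective whatever the code shows, provided that the named structures take their standard form. And the ANCOVA is a sensitivity analysis; it does not supply the confirmatory p-value. One might read the list as a sequence, but the text joins the three with a plain alternative and states no rule.

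**Conclusion.** The point holds as a conditional defect in a contingency rule, plus a wording conflict in the main model. The redundant subject effect does no harm to the Week 6 estimate or standard error; its only cost is a possible needless trigger of the fallback. The fallback rule can give a wrong standard error for the confirmatory test and leaves the choice of structure open.

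Under the assumed SDs in the six tabulated cases, the true level of a nominal 0.05 test runs from 0.086 to 0.031. These figures require that a fallback is actually used and that the Week 6 variance differs from the average over visits. They also assume Week 6 SD 20, complete data and a normal approximation; they are exact under those terms for CS and VC and approximate for AR(1). It is worth correcting because the analysis is confirmatory and the correction is small, not because the planned result is shown to be wrong.

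**What to change.** In SAP 7.6.3:

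- Delete the random-effect sentence, or reword it to say that covariance is unstructured within subject with no separate random effect.
- Replace the fallback sentence with a fixed order of heterogeneous-variance structures, for example heterogeneous Toeplitz, then ARH(1), then CSH, taking the first that converges.
- State that empirical (sandwich) standard errors are used if any fallback is needed.
- Remove VC.

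The particular ladder is a suggestion; what matters is that the order is fixed and that Week 6 keeps its own variance.

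The cost is two sentences and a line of code. SAP section 1 already allows amendments before database lock. Data collection and sample size are untouched, and nothing changes if the unstructured model converges. The downside is slightly wider intervals if a fallback is ever used.

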7.6.4 Sensitivity Analyses for the Primary Efficacy Endpoint

7.6.4.1 Using PP Population

Primary efficacy analysis will be conducted on the PP population as a supportive analysis.

7.6.4.2 Using ANCOVA

The analysis of covariance (ANCOVA) will be conducted for the two primary tests (Dysport 600 U vs. placebo, and Dysport 800 U vs. placebo), with the change of the weekly number of UI episodes from study baseline as response variable, including treatment group, stratification variables [the aetiology of NDO (SCI or MS) and prior intradetrusor BTX-A usage for UI]

Statistical Analysis Plan

Version: Final v1.0

September-2018

Ipsen Protocol No. D-FR-52120-223

000000146513

Date of Issue: 21-

Covance Study ID:

(BTX-naïve or BTX-non-naïve)] and study baseline value of weekly number of UI episodes as covariates.

The least square means (LSMEANS) of the change of weekly number of UI at Week 6 in each group with standard error, the difference of mean between the treatment groups, the 95% CI of the difference and the p-value for treatment group will be presented.

The SAS codes of ANCOVA for reference are below.

CCI [REDACTED]

[REDACTED]

[REDACTED]

[REDACTED]

[REDACTED]

[REDACTED]

[REDACTED]

[REDACTED]

[REDACTED]

[REDACTED]

[REDACTED]

[REDACTED]

[REDACTED]

[REDACTED]

7.6.4.3 Using MI

In presence of missing data in the primary efficacy endpoint, a multiple imputation approach for handling missing data will be undertaken on the mITT population. **CCI** [REDACTED]

[REDACTED]

[REDACTED]

[REDACTED]

[REDACTED]

[REDACTED]

[REDACTED]

[REDACTED]

[REDACTED]

[REDACTED]

[REDACTED]

[REDACTED]

[REDACTED]

[REDACTED]

CCI [REDACTED]

[REDACTED]

[REDACTED]

[REDACTED]

[REDACTED]

[REDACTED]

[REDACTED]

[REDACTED]

[REDACTED]

[REDACTED]

[REDACTED]

[REDACTED]

[REDACTED]

CCI [REDACTED]

[REDACTED]

CCI [redacted]
 [redacted]
 [redacted]
 [redacted]
 [redacted]

In above codes, the variables are defined as:

CCI [redacted]
 [redacted]

7.6.4.4 Using Mis-Stratification Factors

As discussed in Section 5.6.2, the primary endpoint will be analysed with the MMRM using the incorrect stratification factors as recorded in IVRS for the mITT population.

7.6.5 Hierarchical Analysis of Secondary Efficacy Endpoints

As specified in Section 7.6.12, a hierarchical analysis will be performed in the order listed for the following two secondary efficacy endpoints at Week 6 after the first IMP administration:

- 1) Proportion of subjects with no episodes of UI (i.e. continence is achieved)
- 2) Mean change from study Baseline in the I-QoL total summary score

The Derivation rules are specified in Section 3.2 and Appendix II.

For 1), a logistic generalised linear mixed model (GLMM) for repeated measures will be fitted for UI responses using repeated measurements at Week 2, Week 6, and Week 12. The “proportion of subjects with no episodes of UI” will be analysed as a response variable, the model will include treatment group, stratification variables, study baseline value, visit (week 2, week 6 and week 12), study baseline*visit and treatment*visit interactions as fixed effect. The study baseline value will be weekly number of UI episodes. The logistic GLMM is fitted using the logit link and the binomial distribution. Odds ratios, 95% CIs of odds ratio, and p-values for treatment group comparisons at each visit (week 2, week 6 and week 12) will be presented.

The SAS codes of GLMM for reference are below.

CCI [redacted]
 [redacted]
 [redacted]
 [redacted]
 [redacted]
 [redacted]
 [redacted]
 [redacted]
 [redacted]

In above codes, the variables are defined as:

CCI [redacted]
 [redacted]

CCI

For 2), MMRM model will be fitted using the “mean change” endpoint, as the response variable to obtain the p-value of treatment groups. The model will be the same as primary analysis model in section 7.6.3. The least square means of change at Week 6 in each group with standard error, the mean difference of pairwise comparison, the 95% CI of the difference and the p-value for the treatment groups will be presented for each model.

If the testing procedure is stopped at the end of any particular step, the outcomes of the following steps will be presented and used for description only and no formal statistical conclusion will be drawn.

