3.2 Secondary Efficacy Endpoints

The secondary efficacy endpoints are divided into those that relate to parameters measured in the bladder diary, those measured by urodynamic filling cystometry and those that are quality of life measures. From these secondary measures, there are two that have been selected to be analysed as part of a hierarchical testing scheme see Section 3.2.1.

Bladder diary measures:

Mean change from study baseline to post-treatment timepoints in the following variables:

- weekly number of UI episodes (except for week 6 after Treatment 1 which is the primary efficacy endpoint)
- total daily urinary frequency (spontaneous void and CIC)
- daily spontaneous voiding frequency
- daily CIC frequency
- total 24-hour voided volume (spontaneous void and CIC)
- 24-hour voided volume (spontaneous void only)
- 24-hour voided volume (CIC only)
- total volume per void (spontaneous void and CIC)
- volume per void (spontaneous void only)
- volume per void (CIC only)

Proportion of subjects with:

- no episodes of UI (i.e. 100% improvement where continence is achieved)
- UI response at several levels (i.e. $\geq 30\%$ improvement, $\geq 50\%$ improvement, $\geq 75\%$ improvement)

Urodynamic filling cystometry measures (urodynamic subset only):

Mean change from study baseline to week 6 after Treatment 1 in the following variables:

- MCC
- MDP during storage
- Vol@1stIDC (subjects without a post-treatment IDC will have their Vol@1stIDC imputed from their MCC)
- maximum detrusor pressure at first involuntary detrusor contraction (PdetMax@1stIDC)

- end fill pressure (EFP)
- detrusor compliance (DC)

Proportion of subjects with:

- No IDCs (i.e. urodynamic cure is achieved)

Patient-reported outcome questionnaires:

Mean change from study baseline to post-treatment timepoints in the following variables:

- I-QoL total summary score
- I-QoL Score of domain: Avoidance and limiting behaviour
- I-QoL Score of domain: Psychosocial impact
- I-QoL Score of domain: Social embarrassment
- EuroQol 5-dimension 5-level (EQ-5D-5L): Total descriptive score
- EQ-5D-5L: self-rated health (VAS)
- modified patient global impression - improvement (mPGI-I) score (to be assessed at each timepoint without comparison to baseline)

Duration of effect following the first and subsequent treatments

- time to request retreatment
- time to eligibility for retreatment
- time between treatments.

Detailed definitions of all efficacy endpoints are presented in [Appendix II](#).

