- Step 2: The Dysport 600 U and Dysport 800 U will be compared to placebo for the first hierarchical secondary endpoint. Testing will be at the significance level defined in step 1 (0.05 or 0.025). If the p-value associated with this test is lower than the significance level defined in step 1 then it will be considered significant and testing will proceed to step 3. Otherwise the testing procedure will be stopped.
- Step 3: The Dysport 600 U and Dysport 800 U will be compared to placebo for the second hierarchical secondary endpoint. Testing will be at the significance level defined in step 2 (0.05 or 0.025). If the p-value associated with this test is lower than the significance level defined in step 2 then it will be considered significant.

The above testing rules ensure that the hierarchical procedure controls the experiment-wise type one error (i.e. over the three tests) at the 0.05 level for relevant secondary endpoints.

In the event the hierarchical testing procedure is stopped at the end of any particular step, the testing of the following steps will be considered descriptive only and no formal statistical conclusion will be drawn.

Each other secondary endpoint not included within the hierarchical testing procedure will be analysed for exploratory purposes only to compare each Dysport dose to placebo at a 0.05 type one error rate.

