For the DBPC Cycle for I-QOL and EQ-5D-5L, mean change from study baseline to Week 6 and Week 12, will be analysed using MMRM, similar to the primary efficacy analysis. Mean mPGI-I score at Week 2, Week 6, Week 12 will be analysed as a response variable, using MMRM as in the supportive primary analysis, without baseline factor for mPGI-I.

The LS means of change from study baseline in DBPC cycle for I-QoL total summary score at all timepoints will be presented in a line plot by treatment groups up to Week 12.

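### SAP 7.6.5 borrows the primary model for I-QoL, and that model's only named baseline covariate is weekly UI episodes; read literally, the I-QoL baseline is left out

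*SAP*

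**What the plan says.** SAP 7.6.2 places I-QoL inside the controlled testing sequence: "Step 3: The Dysport 600 U and Dysport 800 U will be compared to placebo for the second hierarchical secondary endpoint". SAP 3.2.1 and 7.6.5 identify that endpoint as the change from study baseline in the I-QoL total summary score at Week 6.

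For the model, 7.6.5 item 2 makes the I-QoL change the response and then says "The model will be the same as primary analysis model in section 7.6.3". Section 7.6.3 lists treatment, visit (Weeks 2, 6 and 12), treatment by visit, and then "stratification variables [the aetiology of NDO and prior intradetrusor BTX-A usage for UI] and study baseline value of weekly number of UI episodes". No visible sentence puts the I-QoL baseline in place of, or beside, the UI baseline.

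The I-QoL baseline exists. Protocol Table 8 makes the questionnaire the first procedure at the Treatment Visit, before randomisation and injection, and Table 19 lists that visit as its study baseline. After the first treatment I-QoL is collected at Week 6, Week 12 and end of study, but not at Week 2. The study baseline definition in SAP section 3 (last value up to the day of treatment) covers it, although SAP 3.2.1 labels it a Screening value.

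SAP 7.6.6.3 describes the I-QoL model a second time: "For the DBPC Cycle for I-QOL and EQ-5D-5L, mean change from study baseline to Week 6 and Week 12, will be analysed using MMRM". It calls that model similar to the primary analysis, not the same as it.

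**The concern.** A programmer who follows the prose would adjust I-QoL change for baseline UI episodes and leave out the baseline of the score being analysed. For a change score, its own baseline is usually one of the strongest predictors available, and here it is already in hand at no cost.

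The two readings give different estimates, confidence intervals and p-values for a test that can support a formal claim at 0.05 or 0.025. That choice should be fixed in writing before anyone can see which reading is more favourable. The phrase also cannot be applied completely, because one of the three visits in 7.6.3 has no I-QoL data. The analyst therefore has to depart from it without being told how far.

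**Working it through.** **The plan's own figures.** The documents state no sample size or power for I-QoL. For the primary endpoint, n per group = 2 × SD² × (z₀.₉₈₇₅ + z₀.₈₀)² / Δ² = 2 × 20² × (2.241 + 0.842)² / 9² ≈ 94 by the normal approximation. The noncentral t version gives the stated 96 (power 0.804). That figure is not in question.

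**Inputs.**
- 110 randomised per first-treatment arm and 10% dropout to Week 6 (SAP 2.2 and 2.3): 110 × 0.9 = 99 evaluable per arm.
- Assumed, because the documents give none: correlation r between baseline and Week 6 I-QoL; ratio s of the Week 6 SD to the baseline SD; the role of baseline UI.

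**Formulas** (Week 6, complete data, baseline SD = 1):
- Change score, uninformative covariate: V₀ = s² + 1 − 2rs
- Own baseline as covariate: V₁ = s²(1 − r²)
- Proportional cut: (V₀ − V₁)/V₀ = (1 − rs)² / (s² + 1 − 2rs)

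**Uninformative baseline UI.** Example at s = 1.0, r = 0.5: (1 − 0.5)² / (2 − 1) = 25%, so the literal model with 99 per arm is as precise as an own-baseline model with 99 × 0.75 = 74.

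| s | r = 0.3 | r = 0.5 | r = 0.7 |
|---|---|---|---|
| 0.8 | 50% | 43% | 37% |
| 1.0 | 35% | 25% | 15% |
| 1.3 | 19% | 9% | 1% |

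At s = 1.0 the equivalent numbers per arm are about 64, 74 and 84. If the own-baseline model had 80% power at 0.05, the literal model would have about 62%, 68% and 73%.

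**Baseline UI correlated with baseline I-QoL.** Take s = 1.0, a correlation of −0.5 between the two baselines, and UI related to Week 6 I-QoL only through baseline I-QoL. The literal variance is 2(1 − r) − [0.5(1 − r)]². At r = 0.5 this is 1 − 0.0625 = 0.9375, against 0.75 with own baseline, a 20% cut. Over r = 0.3, 0.5 and 0.7 the cuts are about 29%, 20% and 12%.

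**Baseline UI with a direct effect of its own.** Take UI independent of baseline I-QoL, with partial correlation 0.3 with change given own baseline. The literal variance is V₀ − 0.09V₁.
- Replacing UI by the I-QoL baseline (V₁): at s = 1.0 the cuts are 31%, 20% and 8%. At s = 1.3, r = 0.7 the variance rises from 0.792 to 0.862, about 9%.
- Keeping UI and adding the I-QoL baseline (0.91V₁): in that same corner, 0.862 × 0.91 = 0.784, below both. At s = 1.0, r = 0.5 the variance is 0.91 × 0.75 = 0.6825 against 1 − 0.0675 = 0.9325, a 27% cut.

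Adding is therefore safer than replacing.

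**Error rate.** In 5,000 simulated null trials per setting, rejection at 0.05 was 0.044 to 0.054 with the UI baseline and 0.046 to 0.057 with the own baseline. Neither covariate disturbs type I error.

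**The case against.** The best reply is that the SAP is using shorthand and own baseline was meant all along.

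- Section 7.6.6.3 calls the I-QoL model similar to the primary one.
- The same section analyses mPGI-I "using MMRM as in the supportive primary analysis, without baseline factor for mPGI-I". That exception makes sense if the baseline term belongs to each endpoint, since SAP 3.2 assesses mPGI-I without a baseline comparison.
- Item 1 of 7.6.5 finds it necessary to add "The study baseline value will be weekly number of UI episodes", as if the study baseline value were a slot to be filled.
- The protocol synopsis names the primary model's covariate only as the baseline value.
- The SAP's cross-references are loose: 7.6.5 cites a section 7.6.12 that is not in the contents list, and 7.6.6.1.2 cites the ANCOVA section for an MMRM.
- The model code is blacked out and Appendix II is not visible.

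Most of this stands. A reader might infer that the sponsor will omit the I-QoL baseline; the documents do not support that, and own baseline is the likelier intent. But item 1 names its baseline and item 2, in the same section, does not. Intent inferred from neighbouring sentences does not fix a confirmatory model.

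A reader might also infer that the step-3 test would be invalid. It would not, because the literal model holds its error rate. Nor do the documents support a loss of half the variance. That figure needs an assumed Week 6 SD of 0.8 times the baseline SD with r = 0.3, and no I-QoL SD or correlation is given.

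**Conclusion.** The visible prose, followed as written, leaves a baseline that is already collected out of a confirmatory model, and names a visit at which the endpoint is not measured. This is a wording gap with a likely cost in precision; it does not bias the comparison or weaken error control.

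The illustrative size is about 15% to 35% of the contrast variance for r from 0.7 down to 0.3, with equal SDs and uninformative baseline UI. It is less where baseline UI already stands in for baseline I-QoL, or where the Week 6 SD is larger, and can be close to nothing (1% at s = 1.3, r = 0.7). No figure stated in the plan changes.

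The same wording pattern reaches the continuous urodynamic models (7.6.6.2, through 7.6.4.2). SAP 7.6.6 treats those as exploratory, although Protocol 9.6 plans a hierarchical analysis for some of them. The I-QoL point does not depend on how that difference is resolved.

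This is best classed as a free improvement: worth making, cheap, and harmless if the code already does it.

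**What to change.** Before unblinding, add to SAP 7.6.5 item 2:

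*The study baseline I-QoL total summary score is included as a covariate, in addition to the terms in 7.6.3; visits are Week 6 and Week 12.*

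This keeps baseline UI, the subject effect, the unstructured covariance and the convergence fallbacks of 7.6.3.

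For the exploratory continuous endpoints (7.6.6.1.2, 7.6.6.2, and 7.6.6.3 except mPGI-I), state that the endpoint's own study baseline is included as a covariate. In 7.6.6.1.2, also correct the pointer, which cites ANCOVA section 7.6.4.2 for an MMRM. Section 7.6.6.2 otherwise stays an ANCOVA.

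The cost is about one sentence in each of four sections, plus the corrected pointer, by an amendment that SAP section 1 already allows before database lock. No new data are needed, and the primary model is untouched. If the blacked-out code already uses own baseline, check that it agrees with the new sentence on keeping baseline UI.
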